## PROJECT SUMMARY

In the US alone, millions of cancer patients every year receive chemotherapy with only a 20-60% probability of pathological response, while some experience adverse side effects that lower quality of life without necessarily prolonging it. Reliable identification of ineffective therapies can eliminate needless human suffering while increasing overall probability of positive response to treatment. Chemotherapy resistance profiling entails testing whether a patient exhibits strong resistance to a therapy prior to its final selection by the oncologist. However, there are no effective methods for quickly assessing patient chemotherapy resistance. Patient Derived Xenograft (PDX) models have replaced older Chemotherapy Sensitivity and Resistance Assays (CSRAs) to some degree, but both technologies suffer from long testing times, high cost, and/or low accuracy.

Motility Contrast Tomography (MCT) has recently emerged as a technology that measures the biodynamic response of intact tumor biopsies to applied therapeutics by using Doppler detection of infrared light scattered from intracellular motions inside living tissue. Several small scale animal, xenograft, and human studies have shown this phenotypic profiling technique to be highly accurate in prediction of response and resistance to chemotherapy. This project will be the first human trial of biodynamic phenotyping to predict chemotherapy response among bladder cancer patients. Specifically, the study cohort will include patients selected for neoadjuvant chemotherapy treatment, because this setting offers the opportunity for near-term outcome measurement at the time of post-chemo surgery. Pre-therapy fresh tumor specimens will be imaged using MCT, and the resulting bio-dynamic signatures will be compared to confirmed pathological response at the time of surgery. Observation of a high predictive value will provide the basis for expanded clinical trials and prompt commercialization of a biodynamic chemotherapy selection assay for bladder and other cancer patients.

### Study Schema:

## RATIONALE & BACKGROUND

**STUDY RATIONALE:** The demonstrated ability of MCT to accurately assess tumor xenografts may establish it as a reliable technique for patient tumor stratification based on predicted response to therapy, which could enable a treatment selection based on the personal needs of an individual patient. This study is designed to assess MCT as an assay for predicting chemosensitivity to treatment with chemotherapy agents routinely used in the neoadjuvant and adjuvant treatment of bladder cancer. If positive, the results of this study will provide the basis for expanded clinical trials and use of MCT in therapy selection.

**BACKGROUND:** Live cell imaging has become the standard for high-content analysis and drug discovery applications. The most common assays on live cells include viability, proliferation and cytotoxicity assays as cellular physiology and function are measured responding to applied perturbations of xenobiotics. Cellular and tissue viability assays are typically measured using exogenous vital dyes as biomarkers of membrane integrity or cellular metabolic activity. However, dyes are invasive, potentially toxic, and often require fixing of the tissue or permeabilization of the membranes [1, 2]. Furthermore, the common format of high content analysis and flow cytometry requires isolated cells, or cells distributed on flat hard surfaces. Isolated cells lack many of the biologically-relevant intercellular connections and communications that are hallmarks of healthy tissue [3, 4], and flattened cells on plates have pathological shapes and anisotropic cellular adhesions [5].

Discovery of technology that can predict response to cancer therapy is an urgent priority. While many technologies exist to evaluate early response to drugs *ex vivo*, the need to perform viability, cytotoxicity and proliferation assays in three-dimensional tissue or culture has become increasingly urgent [6, 7], as drug response in 2D is often not the same as drug response in biologically-relevant three dimensional culture. This is in part because genomic profiles are not preserved in monolayer cultures [8-10]. There have been several studies that have tracked the expression of genes associated with cell survival, proliferation, differentiation and resistance to therapy that are expressed differently in 2D cultures relative to three-dimensional culture. For example, cell lines of epithelial ovarian cancer [11, 12], hepatocellular carcinoma [13-15] or colon cancer [16] display expression profiles more like those from tumor tissues when measured in three-dimensional culture, but not when grown in 2D. In addition, the three-dimensional environment of 3D culture presents different pharmacokinetics than 2D monolayer culture and produce differences in cancer drug sensitivities [17-20]. Finally, most current technologies rely on destructive end-point assessment, preventing meaningful longitudinal observation of therapy response over time.

[figure not shown]
One of the main challenges to migrating drug-response assays to the third and fourth dimensions has been to find a means to extract vital information from deep (up to a millimeter) inside living tissue. Tissue is translucent and light can propagate diffusively many centimeters. Furthermore, the dynamic motions of living cells cause dynamic light scattering that produces phase fluctuations on the scattered light fields that can be measured as dynamic speckle in diffusely reflected light from tissue. This is the basis of diffusing wave spectroscopy (DWS) [21, 22] and diffusion correlation spectroscopy (DCS) [23-26], but these techniques lack depth resolution. A powerful tool in the characterization of light propagation in tissues is the use of interferometry [27]. Interferometric detection is the underlying process in optical coherence tomography (OCT) [28-31], which is a point-scanning technique that suppresses speckle [32-34], although speckle decorrelation in OCT data can provide similar information as provided by DCS. This has been used to measure intracellular rheology [35] and to find dynamic signatures of apoptosis [36]. Transport also can be detected at cellular resolution using phase contrast microscopy [38], but this approach cannot be used in thick tissues.

[name] and colleagues have developed volumetrically-resolved tissue dynamic imaging that uses the advantages of depth selectivity from low-coherence interferometry, combined with high speckle contrast in broad-illumination digital holography. The technique is called Motility Contrast Tomography (MCT) and uses low-coherence digital holography to penetrate up to 1 millimeter into living tissue to measure speckle dynamics from light scattering from dynamic motion in living cells [37]. It was previously applied as a cytotoxicity assay to study the efficacy of anti-mitotic drugs [40]. In essence, the technology works by profiling the ‘movement’ of cellular organelles. Specific changes in organelle motion are detectable very early in cells undergoing response to chemotherapy treatment, and may be usable as an early predictor of chemotherapy response.

MCT is based on optical coherence imaging (OCI) [38]. OCI is a full-field short-coherence holography [39] that collects backscattered speckle. With the help of coherence gating, OCI can optically section tissue up to 1 mm deep. MCT specifically uses intracellular motion as the endogenous contrast to characterize submicron subcellular motion inside three-dimensional living tissue [42].

Figure 1 shows the holographic recording principle of MCT. After calibration, the short coherence light is first divided into an object beam and a reference beam. The object beam hits the living tissue sample, and backscattered speckles from the tissue are collected by the lens L1. The living tissue sample locates at the focal plane of the lens L1, so L1 also performs an optical Fourier transform of the backscattered light. The charge coupled device (CCD) locates at the other focal plane of L1, so it captures the Fourier transformed scattering light from the tissue. The reference beam is controlled by a delay stage (not shown in the figure) to adjust the path length of the reference beam to perform a zero-path match between the object and reference beams. The beam splitter combines both beams and because they are zero-path matched, they interfere at the CCD plane. The reference beam is tilted by  $20^\circ$  in an off-axis configuration, and the spacing of the interference fringes ( $\Lambda$ ) is 3 pixels ( $24 \mu\text{m}$ ). The speckle size (aspec) is adjusted to be 3 fringes wide ( $70 \mu\text{m}$ ). Additional details about the experimental setup can be found in reference [41].

Fig.1. The principle of MCT on multicellular tumor spheroids. The biological sample is located at the image plane of lens L1. The back scattered light from the sample is Fourier transformed by L1 and interfered with reference beam on the CCD chip. The speckle hologram is recorded on the Fourier plane with a  $20^\circ$  crossing angle with the reference beam. Examples of a) Raw digital hologram; b) reconstructed image; c) MCI image. O.A.: optical axis; I.P.: image plane; L1: lens; BS: beam splitter; CCD: charge coupled device.

**EX VIVO CANCER CHEMOSENSITIVITY ANALYSIS** MCT was previously applied to study the efficacy of anti-mitotic drugs using multicellular tumor spheroids [40]. When applying MCT to tumor xenografts, it is also capable of showing a significantly different response between two cell lines under cisplatin. After applying the drug, the normalized standard deviation (NSD) value of the platinum-sensitive cell line (A2780) drops from 0.7 to 0.1 in 8

hours. In contrast, the NSD value of the platinum-resistant cell line (A2780-CP70) remains nearly constant (0.81 to 0.80) 9 hours after applying drug. The NSD value of normal mouse tissue attached to the tumor xenograft decreases only a little (0.6 to 0.52) compared with A2780. Fig. 2 shows the cisplatin drug response curves. The NSD value of each point is averaged over the entire target. The time between measurements is 24 minutes for A2780-CP70 and normal mouse tissue and is 12 minutes for A2780. The 20  $\mu\text{M}$  cisplatin was applied at time  $t = 0$ , and the measurements lasted 9 hours for A2780-CP70 and normal mouse tissue, and lasted 8 hours for A2780. At time=0, the aggressive cell line A2780-CP70 has the highest NSD and the normal mouse mesenterium tissue has lowest NSD (0.6). The NSD of the platinum-sensitive cell line A2780 lies in the middle: 0.7. After applying cisplatin, the NSD curve of A2780 drops immediately. The NSD value of the A2780-CP70 almost doesn't change.

[figure not shown]

Fig. 2 Motility metric (NSD) of ovarian cancer tumor xenografts responding to 20  $\mu\text{M}$  cisplatin. The x-axis is time (minute), the y-axis is NSD value. The sensitive tumor is A2780, while the insensitive tumor A2780-CP70. Both tumor tissues begin with higher motility than normal mouse tissue. The cisplatin was added at time  $t=0$ . The NSD of A2780 dropped very fast and after 8 hours it dropped to 0.1. The NSD of the insensitive tumor A2780-CP70 didn't change during 9 hour period. The NSD of normal mouse tissue dropped a little compared with the A2780.

In a further study in a veterinary clinical setting, MCT has been used to predict patient outcome for canine non-Hodgkin's lymphoma. Canine non-Hodgkin's lymphomas are initially characterized by tumoral infiltration of peripheral lymph nodes. Canine non-Hodgkin's lymphomas are diverse in their clinical aggressiveness and response to chemotherapy. The only current biomarker for chemoresponsiveness is tumor cell immunophenotype (i.e. T-cell vs. B-cell origin), but chemoresponsiveness varies tremendously within immunophenotype, which reduces the clinical utility of this biomarker. In our study, we used MCT to measure the heterogeneous response of canine lymphoma biopsies to the standard-of-care doxorubicin. The biodynamic signatures of doxorubicin responsivity ex vivo were correlated with canine patient outcome. These studies have demonstrated, for the first time, the utility of label-free intracellular biodynamic markers to predict therapeutic efficacy for cancer treatment in dogs.

## SPECIFIC AIMS

The primary study objective is to examine the feasibility of using MCT as a chemosensitivity assay among bladder cancer patients receiving neoadjuvant chemotherapy by comparing MCT patterns consistent with chemotherapy response or resistance ex-vivo to confirmed response or resistance to chemotherapy as measured by Response Evaluation Criteria in Solid Tumors (RECIST) v1.1 criteria.

**PRIMARY ENDPOINT:** Objective pathological response measured at the time of surgery.

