## RESEARCH DESIGN AND METHODS

**STUDY DESIGN:** Retrospective correlation study.

**PARTICIPANT IDENTIFICATION:** Patients of all races and ethnic groups are eligible for this study. Patients will be recruited from participating sites after interpretation of initial cystoscopy and/or radiological screening, but prior to performance of a second staging biopsy and/or Transurethral Resection of Bladder Tumor (TURBT) procedure per standard of care. Pre-screening of potential participants may be performed by the principal investigator or delegates under the principal investigator's direct supervision. Once all eligibility criteria are confirmed, potential participants will be offered the opportunity to participate. Potential participants will be presented with the purpose of the study and the potential risks and benefits of participation. All potential participants who are interested in participation will undergo the informed consent process privately at the time of their appointment or during a return appointment after they have an opportunity to review the consent. Participants will be considered registered to the study upon receipt of a signed informed consent statement and determination by the principal investigator post-cystoscopy procedure that sufficient tumor tissue will likely be available to allow for excess specimen to be used in the study.

Registration information will be maintained by the Principal Investigator. All participants will be assigned a unique study ID derived from the bar-coded specimen collection kit used to collect all specimens in the study. All subjects will adhere to inclusion and exclusion criteria as listed below.

**INCLUSION CRITERIA:** To be eligible for the study, patients must meet the following criteria:

1. Ability to understand and willingness to sign an informed consent and authorization for release of tissue not required for pathologic diagnosis to be used for research purposes
2.  $\geq 18$  years old at time of consent
3. Suspected muscle-invasive cancer and/or high probability of receiving neoadjuvant chemotherapy and a cystectomy

**EXCLUSION CRITERIA:** To be eligible for the study, patients must not have any of the following:

1. Women who are pregnant or breastfeeding
2. Known tumor genetics, comorbidities or other factors, which in the treating physician's professional judgement, make the patient an unlikely candidate to receive neoadjuvant chemotherapy or a cystectomy.

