## MEASUREMENT OF EFFECT - CHEMOTHERAPY

**Timing of response assessment:** In addition to a baseline scan (obtained within 35 days prior to registration), patients' response to chemotherapy will be evaluated immediately upon surgical tumor resection per routine care guidelines and according to institutional practice.

**Methods of response assessment:** Response and progression will be evaluated in this study using the new international criteria proposed by the revised RECIST guideline (version 1.1). Changes in the largest diameter (unidimensional measurement) of the tumor lesions are used in the RECIST criteria.

**Evaluable for objective response:** Only those patients who have measurable disease present at baseline, have received at least one cycle of neoadjuvant chemotherapy, and have had their disease re-evaluated upon surgical tumor resection will be considered evaluable for response. These patients will have their response classified

according to the definitions stated below. (Note: Patients who exhibit objective disease progression prior to the end of cycle 1 will also be considered evaluable.)

**Evaluable Non-Target Disease Response:** Patients who have lesions present at baseline that are evaluable but do not meet the definitions of measurable disease, have received at least one cycle of therapy, and have had their disease re-evaluated will be considered evaluable for non-target disease. The response assessment is based on the presence, absence, or unequivocal progression of the lesions.

**Measurable disease:** Measurable lesions are defined as bladder lesions that can be accurately measured in at least one dimension (longest diameter to be recorded) as  $\geq 2$  cm by cystoscopy or CT scan, MRI, or calipers by clinical exam. All tumor measurements must be recorded in millimeters (or decimal fractions of centimeters).

**Non-measurable disease:** All other lesions (or sites of disease), including small lesions (longest diameter  $< 2$  cm), are considered non-measurable disease for purposes of this study.

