**Target lesions:** Any measurable bladder lesions up to a maximum of 2 lesions per bladder and 4 lesions in total, should be identified as target lesions and recorded and measured at baseline. Target lesions should be selected on the basis of their size (lesions with the longest diameter), be representative of all lesions, but in addition should be those that lend themselves to reproducible repeated measurements. It may be the case that, on occasion, the largest lesion does not lend itself to reproducible measurement in which circumstance the next largest lesion which can be measured reproducibly should be selected. A sum of the diameters (longest for non-nodal lesions, short axis for nodal lesions) for all target lesions will be calculated and reported as the baseline sum diameters. The baseline sum diameters will be used as reference to further characterize any objective tumor regression in the measurable dimension of the disease.

**Non-target lesions:** All other lesions (or sites of disease) including any measurable lesions over and above the target lesions should be identified as non-target lesions and should also be recorded at baseline. Measurements of these lesions are not required, but the presence, absence, or in rare cases unequivocal progression of each should be noted throughout follow-up.

**Methods for Evaluation of Measurable Disease:** All measurements should be taken and recorded in metric notation using a ruler or calipers. All baseline evaluations should be performed as closely as possible to the beginning of treatment and never more than 4 weeks before the beginning of the treatment.

---

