## RESPONSE CRITERIA

**Complete Response (CR):** Disappearance of all target lesions. Any pathological lymph nodes (whether target or non-target) must have reduction in short axis to  $< 10$  mm.

**Partial Response (PR):** At least a 30% decrease in the sum of the diameters of target lesions, taking as reference the baseline sum diameters.

**Progressive Disease (PD):** At least a 20% increase in the sum of the diameters of target lesions, taking as reference the smallest sum on study (this includes the baseline sum if that is the smallest on study). In addition to the relative increase of 20%, the sum must also demonstrate an absolute increase of at least 5 mm. (Note: the appearance of one or more new lesions is also considered progression.)

**Stable Disease (SD):** Neither sufficient shrinkage to qualify for PR nor sufficient increase to qualify for PD, taking as reference the smallest sum diameters while on study.

---

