## STATISTICAL CONSIDERATIONS

**STUDY DESIGN:** This is a non-randomized, multi-arm, multi-center, feasibility study, designed to examine the feasibility of using MCT as a chemosensitivity assay among bladder cancer patients by comparing ex-vivo MCT patterns consistent with chemotherapy response and resistance to confirmed pathological response or resistance as measured by Response Evaluation Criteria in Solid Tumors (RECIST) v1.1 criteria.

**DEFINITION OF PRIMARY OUTCOME ENDPOINT:** Feasibility is defined as a high statistical correlation between MCT-predicted response, and surgically confirmed response to neoadjuvant chemotherapy.

**ANALYSIS PLAN FOR PRIMARY OBJECTIVE:** The study will be considered successful, if a majority of specimens yield interpretable MCT results, and if MCT signatures are identified which demonstrate a high statistical correlation to confirmed patient response.

**EXPLORATORY ANALYSIS:** Due to the inadequate samples size, no formal analysis is planned. Descriptive analysis of the correlation between MCT parameters and clinical outcome measures will be performed.

**DETERMINATION OF SAMPLE SIZE:** A target sample size of 500 patients was selected for initial enrollment using the investigators' previous research experience to approximate the appropriate number needed to demonstrate the feasibility of this technique. It is anticipated that only 20-30% of enrolled patients will yield specimens evaluable for response. It is estimated that it will take approximately 6-12 months to complete accrual.

**EVALUATION FOR RESPONSE:** Participants who provide a bladder tumor specimen, have received at least one cycle of chemotherapy, and have had their disease re-evaluated upon surgical resection will be considered evaluable for response.

**REPLACEMENTS:** Participants who withdraw from the study prior to having the TURBT procedure or fail to complete at least one evaluation for response will be replaced. No reported data will be included for participants who are replaced.

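### The primary endpoint is named pathological response but measured by RECIST lesion rules, and the baseline windows, baseline reference and evaluable definitions behind it conflict

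*Protocol*

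**What the plan says.** **Endpoint.** Specific Aims names the primary endpoint as "Objective pathological response measured at the time of surgery". The objective just above it compares MCT with "confirmed response or resistance to chemotherapy as measured by Response Evaluation Criteria in Solid Tumors (RECIST) v1.1 criteria". Statistical Considerations joins the two ideas as "confirmed pathological response or resistance as measured by Response Evaluation Criteria in Solid Tumors (RECIST) v1.1 criteria", and the outcome item in Appendix B does likewise. The only written categories, under Response Criteria, are CR, PR, SD and PD by lesion diameters, nodal short axis and new lesions; PR is "At least a 30% decrease in the sum of the diameters of target lesions, taking as reference the baseline sum diameters". Measurement of Effect - Chemotherapy adds a non-target route based on presence, absence or unequivocal progression.

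**Baseline.** The timing paragraph of that section reads "In addition to a baseline scan (obtained within 35 days prior to registration", closing the bracket there. The later paragraph on evaluating measurable disease reads "All baseline evaluations should be performed as closely as possible to the beginning of treatment and never more than 4 weeks before" treatment begins.

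**Registration and TURBT.** Under Participant Identification, registration needs signed consent and a post-cystoscopy judgement that "sufficient tumor tissue will likely be available to allow for excess specimen to be used in the study". The replacement rule covers "Participants who withdraw from the study prior to having the TURBT procedure".

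**Evaluable.** Measurement of Effect - Chemotherapy requires measurable disease (2 cm or more), one cycle and re-evaluation at resection. It gives smaller lesions the non-target route and adds a note admitting progression before the end of cycle 1. Statistical Considerations requires a specimen, one cycle and re-evaluation at resection. It states no measurability rule and does not repeat the note.

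**The concern.** Part of the success criterion in Statistical Considerations is a high statistical correlation between MCT signatures and confirmed response, so even a descriptive result depends on how the response label is made. One site could work from the cystectomy report and another from the diameter rules. Both could claim to follow the protocol while classing the same patient differently. Sites could also differ on which baseline supplies the reference sum, and on whether a patient counts at all.

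The baseline question matters because a resection takes place between the registration-based scan and chemotherapy. On that reference, the label mixes surgical removal with drug effect, and MCT is meant to predict only the latter. Early progressors are the other sensitive group, because they carry information on resistance.

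**Working it through.** The plan attaches no figure to this point. The only related arithmetic is the number of patients the label would apply to: 500 × 0.20 = 100 to 500 × 0.30 = 150.

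**1. Name against rule.** The objective, the methods of assessment, the response criteria, the statistical section and Appendix B all point to RECIST v1.1. No section defines a pathological category such as residual stage, a tumour-free specimen or downstaging. The Data Collection list has an objective-response item, and CT scans only where available. It does not list the cystectomy pathology report, which Appendix B does request.

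**2. Baseline windows.** Count days from registration (day 0). Let *s* be the scan day and *T* the days from registration to the start of chemotherapy, *T* ≥ 0.
- First rule: −35 ≤ *s* ≤ 0, which gives 36 possible days.
- Second rule: *s* ≥ *T* − 28.
- Days meeting both: 0 − (*T* − 28) + 1 = 29 − *T* for *T* = 0 to 28, and none for *T* ≥ 29.

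| *T* (days) | Scan days meeting both rules, of 36 |
|---|---|
| 0 | 29 |
| 14 | 15 |
| 21 | 8 |
| 28 | 1 |
| 29 or more | 0 |

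Because *T* cannot be negative, days −35 to −29 always fail the second rule. The protocol does not give *T*; the rows are a range, not an estimate.

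**3. Which side of the TURBT.** At registration the availability of tissue is still a forecast, and the replacement rule provides for withdrawal before the TURBT. Registration therefore precedes the study TURBT, and so does a scan taken before registration. The second rule asks for a baseline as near to treatment as possible, which points to a later and possibly post-TURBT assessment. Nothing says which one supplies the baseline sum.

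**4. Effect of a pre-TURBT reference.** If the TURBT cuts the diameter by a fraction *c*, PR needs a final diameter of at most 0.7 of the pre-TURBT value. Further shrinkage needed = 1 − 0.7/(1 − *c*).
- *c* = 0.10: 1 − 0.7/0.9 = 22.2%
- *c* = 0.20: 1 − 0.7/0.8 = 12.5%
- *c* = 0.30: 1 − 0.7/0.7 = 0%

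Example with assumed sizes: 30 mm before TURBT, 24 mm after, 21 mm at surgery. Against 30 mm the change is 1 − 21/30 = 30%, a PR. Against 24 mm it is 1 − 21/24 = 12.5%, stable disease.

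For a sphere (assumed), these cuts mean removing 1 − 0.9³ = 27%, 1 − 0.8³ = 49% and 1 − 0.7³ = 66% of the volume. The 80 mg research sample is negligible: at an assumed 1 mg/mm³, a 20 mm sphere holds 4,189 mm³, so 80 mg is 1.9% of it and lowers the diameter by 0.6%.

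The choice of baseline also affects the route. A 10% cut takes a lesion smaller than 20/0.9 = 22.2 mm below the 2 cm limit, and a 20% cut does so below 20/0.8 = 25 mm.

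**5. Evaluable definitions.**

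| Patient | Measurement of Effect | Statistical Considerations |
|---|---|---|
| Lesion under 2 cm, specimen given, one cycle, resected | Non-target route only | Evaluable, route not stated |
| No visible lesion at a post-TURBT baseline, specimen given, one cycle, resected | Neither route | Evaluable |
| Progression before the end of cycle 1 | Evaluable by the note | Not mentioned |

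The second row arises only if a post-TURBT baseline is used.

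**The case against.** The strongest reply is that RECIST is cited consistently and its categories are written out, so the endpoint is badly named rather than undefined. That is right. A reader might infer that there is no usable endpoint, and the text does not support that. What stands is the conflict between name and rule, which lets a site work from either. An SAP, not shown here, might add a pathological cut-off, but the protocol's own sections would still disagree.

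A reader might also infer that Statistical Considerations excludes early progressors. It does not say that only patients meeting its conditions are evaluable, so the earlier note can be read as adding to it. The accurate statement is that their status is ambiguous. The ambiguity has a consequence: participants who do not complete a response evaluation are replaced and their data left out.

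The two windows have different anchors, and many scans meet both when chemotherapy starts soon after registration. Lesions may also be measured by cystoscopy or calipers, so a registration scan plus a later baseline measurement is possible. The conflict is certain only for days −35 to −29 and for long intervals.

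Finally, it is tempting to conclude that TURBT materially inflates response in this study. The documents do not show that. The Pre-Treatment Biopsy Plan says the whole tumour is often not resected, the 30% diameter cut needs about two thirds of the volume removed, and the 4-week rule leans towards a later baseline. The mechanism stands; its frequency is unknown.

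The study is non-interventional and its exploratory analysis is descriptive. That limits the harm, but the headline result is still an association with this label.

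**Conclusion.** The point holds as a conflict of definitions on the primary endpoint and should be corrected before any MCT comparison. The endpoint's name and its rules do not match. The baseline windows cannot both be met for scans 29 to 35 days before registration, or for any single scan once chemotherapy starts more than 28 days after it. The reference relative to TURBT is not settled, and the two evaluable definitions differ on measurable disease and are unclear on early progressors.

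The window result follows from the two rules alone, apart from the unstated interval *T*. The PR thresholds follow from the 30% rule, with the diameter cuts assumed. The volume figures assume a sphere. No size of bias in the MCT association can be derived from the documents. The other half of the success criterion, that most specimens give interpretable MCT results, is not affected.

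**What to change.** State one operational primary endpoint in Specific Aims, Measurement of Effect - Chemotherapy, Response Criteria, Statistical Considerations and Appendix B, fixed before any MCT comparison. Either route reconciles the text:
- **Keep pathological response**, as the name implies. Base it on the cystectomy report against the TURBT report, with a cut-off chosen by the sponsor, and report RECIST change separately.
- **Keep RECIST.** Rename the endpoint, and reference change to a post-TURBT, pre-chemotherapy assessment where one exists.

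Under either route:
- Merge the two baseline rules into one window, and say which assessment supplies the baseline sum.
- Merge the two evaluability texts into one definition that says how patients who progress before surgery are classed.
- Add the cystectomy pathology report, already requested in Appendix B, to the Data Collection list.
- Record TURBT completeness (complete, incomplete, not recorded) from the TURBT clinical description already on that list, and report the MCT association by it. Resection before chemotherapy can affect either version of the label.

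The cost is an IRB-approved amendment and a few data items, with no new procedure. Fewer patients may have a RECIST result, completeness may be missing for some, and the TURBT effect will be described rather than removed.
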